Background: Transcatheter Aortic Valve Implantation (TAVI) is a method where an artificial heart valve is implanted through a. femoralis (the groin) or via alternative access (apical, trans caval, axillaris, direct aorta), instead of conventional surgery. TAVI is the routine treatment for in-operable and high-surgical risk patients, and is increasingly used in patients with low and intermediate surgical risk (1, 2). In Denmark, approximately 1000 TAVI valves are implanted each year. In Europe yearly implantation mounts to more than 50.000 TAVI devices. Although a considerable number of TAVI valves have been introduced, there are few direct comparisons of the valves. The 5 most widely used valves are: Sapien (Edwards)(2), Evolut (Medtronic) (3), Navitor/Portico (Abbott) (4, 5) and Acurate (Boston) (6, 7). New TAVI-valves are routinely introduced to the market. Recently, Myval (Meril) (8) and Allegra (New Valve Technology) (9) were launched.

The larger TAVI-centers are routinely using 2-4 different valves, and the majority of patients are eligible for treatment with more than one valve.

The purpose of the “Compare-TAVI” organization is to ensure a continuous comparison of the TAVI-valves implanted, and to monitor long-term valve performances.

Purpose: To compare outcome in patients randomized to treatment with one of two TAVI-valves.

Hypotheses:

1. There is no difference in the combined endpoint (death, stroke, moderate/severe para-valvular leakage, moderate/severe valve deterioration) between the two valves being compared.
2. There is no difference between valves in secondary endpoints: death, stroke, moderate/major paravalvular leakage, moderate/severe valve deterioration, new pacemaker implantation, readmission for congestive heart failure, 6-minute walk test, and degeneration of the valve as evaluated by

computerized tomography (CT), transthoracic echocardiography (TTE), transesophageal echocardiography (TEE), or MRI.

Design: Randomized controlled trial with clinical and national registry follow-up.

Inclusion criteria:

1. Patient more than 18 years of age.
2. Patient eligible for at least 2 valves being implanted routinely at the participating center, according to a TAVI heart team conference.
3. The center experience for each of the valves considered should be more than 15 cases a year, and the treating physician should have implanted at least 15 of each valves used in the trial.
4. The center volume should be more than 75 cases a year.

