5. The patient has given signed informed consent.
6. TAVI performed via the femoral artery.

Centers eligible for inclusion: Scandinavian and European centers who fulfill the above mentioned criteria.

Randomization:

Before randomizing patients, the center decides which two valves the patient is found eligible for, and enters these valves in the electronic randomization form (TrialPartner). Randomization is then performed between these two valves. A patient is only randomized if a dedicated technical TAVI conference has found the patient eligible for treatment with both valves.

Consecutive cohorts are established.

We plan to initiate the following cohorts:

Cohort A: Patients randomized to the Sapien or the Accurate neo 2 TAVI valve (Approved, not recruiting, await funding).

Cohort B: Patients randomized to the Sapien or the Myval TAVI valve (Recruiting).

Cohort C: Patients randomized to a BEV valve (To be determined whether Sapien or Myval) compared to the Navitor valve (Awaits approval and funding).

Operator requirements:

Any procedure requires that the physician has performed at least 15 implantations with the valve in use. Otherwise the procedure is performed according to the routine of the institution.

Primary endpoints, for each cohort:

1. MACE: Mortality, stroke, moderate/major PVL, moderate/severe valve deterioration at 1 year, using VARC-3 criteria (10).

Secondary endpoints, for each cohort:

1. MACE: Mortality, stroke, moderate/major PVL, moderate/severe valve deterioration at 30-day, 3-year, 5-year and 10-year, using VARC-3 criteria (10).
2. Mortality: 30-day, 1-year, 3-year, 5-year and 10-year.
3. Stroke: During admission, 30-day, 1-year, 3-year, 5-year and 10-year, using VARC-3 criteria (10).
4. Moderate or severe PVL: 30-day, 1-year, 3-year, 5-year and 10-year, using VARC-3 criteria (10).
5. Moderate or major valve deterioration: 30-day, 1-year, 3-year, 5-year and 10-year, using VARC-3 criteria (10).
6. Pacemaker-implantation: during admission, 30-day, 1-year, 3-year, 5-year and 10-year.
7. Major bleeding resulting in drop in hgb-level ≥ 1.86 mmol/l and/or erythrocyte transfusion ≥ 2 units: during admission, 30-day, 1-year, 3-year, 5-year and 10-year, modified from BARC type 3-5 criteria (11, 12).
8. 6-minute walk test: baseline, 30-day, 1-year, 3-year, 5-year and 10-year.

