25. CABG (not scheduled before TAVI), 30-day, 1-year, 3-year, 5-year and 10-year according to VARC-3 criteria (10).
26. Reoperation (TAVR, SAVR, BAV), 30-day, 1-year, 3-year, 5-year and 10-year according to VARC-3 criteria (10).
27. Newly diagnosed atrial fibrillation/flutter, 30-day, 1-year, 3-year, 5-year and 10-year according to VARC-3 criteria (10).

Registration of endpoints:

The majority of endpoints are collected from national registries. An echo core-lab is established to evaluate echo parameters (degree of PVL moderate/severe, valve deterioration, thrombosis). A CT core-lab is established to evaluate CT parameters (leaflet thickening, reduced leaflet motion, leaflet thrombosis, coronary alignment). An MRI core lab is established to evaluate MRI parameters (EOA and volume of aortic regurgitation). A separate core lab is established for analysis of aortaograms (videodensitometry) following TAVI. Procedure-related complications are manually collected from electronic patient files. At each follow-up (1-month, 1-year, 3-year, 5-year, 10-year) each site also monitor events and file them in the ECRF, thus both site-reporting and registry-validation of events. Selected endpoints are adjudicated by an endpoint committee (Stroke, AMI, readmission with heart failure, endocarditis).

Power calculations:

For each cohort (randomized comparison between two valves) the steering committee decides to perform the study with or without interim analyses. In case interim analyses is chosen, a safety committee will compare outcome after inclusion of approximately 1/3 and 2/3 of patients (interim analyses). If one valve is

not clearly inferior, randomization will continue until the complete cohort is included. The size of the cohort is dependent of expected event-rate, chosen non-inferiority margin, number of interim analyses and expected drop-out. See table below. With 2 interim analyses and a non-inferiority margin of 4%, event rate 9% and expected drop out of 5% the sample size should be 1346 patients. If including 1062 patients as planned in cohort B, and with no interim analyses and 5% drop-out, the non-inferiority margin would be 4% if the event-rate is 7% and 4.5% if the event rate is 9%. If the observed event-rate differ significantly from the expected, the steering committee should consider adjusting sample size or non-inferiority margin (see table below).

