Table: Various event-rates, non-inferiority margins and sample sizes estimated for non-inferiority studies with and without drop-out, and with and without interim analyses. Power=0.80. Alfa=0.05.

Event rate	Non-inferiority margin	Relative non-inferiority margin	No drop-out, No interim-analysis	No drop-out, 2 interim-analyses	5% drop-out, no interim-analyses	5% drop-out, 2 interim-analyses
Closest non-inferiority margin (1.decimal) if no. of included patients is 1062, without interim-analyses and with 5% drop-out (As planned in cohort B)						
7	≈4.0	0.57				
9	≈4.5	0.50	1009	1017	1062	1071
11	≈5.0	0.45				
13	≈5.3	0.41				
Closest non-inferiority margin (1.decimal) if no. of included patients is 1345, With interim analyses and 5% drop-out (As planned in cohort A)						
7	≈3.6	0.52				
9	≈4.0	0.44	1268	1279	1336	1346
11	≈4.4	0.40				
13	≈4.7	0.36				
Study size if fixed non-inferiority margin = 4%						
7	4	0.57	1008	1017	1062	1070
9		0.44	1268	1279	1335	1346
11		0.36	1514	1527	1594	1607
13		0.31	1750	1764	1843	1857
Study size if fixed non-inferiority margin = 4.5 %						
7	4.5	0.64	796	803	838	845
9		0.50	1002	1011	1055	1064
11		0.41	1198	1208	1262	1272
13		0.35	1382	1394	1455	1467

For the MRI-substudy evaluating the hemodynamics (EOA, aortic regurgitation fraction), the expected EOA is 1.5 (SD 0.54) cm², and the expected regurgitation fraction 0.14 (SD expected to be 0.09). A total of 148 patients are needed to document a difference of 0.25 cm² in EOA (1.5 to 1.25 cm²) and 102 patients to document a difference of 0.05 in expected regurgitation fraction (0.14 to 0.09). The initial plan was to include 166 patients with an expected drop-out of 10% of patients. After inclusion of the first 166 patients in the MRI-substudy, inclusion was on hold for 1 year, and Myval was replaced by Myval Octacor. It was therefore decided to include another cohort in the MRI-substudy, comparing Sapien with Myval Octacor. To account

for higher than expected drop-out, the ethical committee was applied and approved that the MRI-substudy cohort was increased up to 360 patients. A HCT-substudy is performed with expected 850 patients evaluating occurrence of HALT at 1-month and 1-year. This substudy is descriptive.

Criteria used to perform interim analysis before planned or terminate the study before planned:

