For each cohort the maximal inclusion period is 3 years, and the first interim analysis (if planned according to the steering committee) will be performed after no later than two years of inclusion. A cohort will also be closed for inclusion, if one of the study valves is retracted from the market or replaced by a new generation of the device.

Number of centers and procedures per center: The prerequisite for initiating a comparison between two valves is that at least 3 centers will randomize from the beginning, that at least 10 centers are expected to randomize in each cohort, and that each center aims at including at least 50 patients per year.

Statistics: Data will be analyzed according to the intention-to-treat principle. Continuous data will be presented as mean \pm SD, and compared using a t-test, if data are normally distributed. If data are not normally distributed the Mann Whitney U test will be used. Categorical variables will be compared using Fischers exact test or Chi-square test as appropriate, and data presented as numbers and percentages. Significance level is $p<0.05$ (double sided). When comparing primary endpoints, a non-inferiority analysis will be used. When comparing secondary endpoints, Cox regression and logistic regression analyses will be used, as appropriate. Kaplan-Meir curves will be used for graphical presentation of time to events.

Data management: Data will be collected and stored according to the Danish data protection legislation. TrialPartner will be used for the Electronic Case Report form (ECRF). Patient and procedural characteristics will be entered in the ECRF following the procedure and at time of discharge. Follow-up (30-day, 1-year, 3-year, 5-year and 10-year) will be conducted mainly registry based (CPR-registry, National patient registry, Invasive registry), but at each follow-up the site will also check for events, and file them in the ECRF. This will ensure two sources for event-registration. Regarding moderate and severe PVL, moderate and severe aortic stenosis, and presence of thrombus or leaflet thickening, data will be entered by the Echo and HCT core labs. MRI findings will be entered by the MRI core lab. TrialPartner is approved by the Danish data regulative, and data entry and access will be logged. When a cohort is terminated, data will be merged and anonymized and a key stored with the CPR-number.

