Recruitment of patients and informed consent: Patients admitted for a TAVI procedure will be asked for inclusion in the study. No announcement will be performed. There is no economical compensation to the patients, except that transportation expenses can be covered for the follow-up visits. Patients will receive information regarding the study either in the out-patient clinic, or when they are admitted for preoperative assessment. The information will be given by a nurse, instructed by the investigator, or by the treating physician. Patient information will be written and oral. The patient will be informed that they may have time to consider inclusion, that a relative or a third person may participate, when information regarding the study is given. The patient is informed, that they may withdraw their consent at any time. All patients have been given written and oral information regarding the purpose, procedure, risk and benefit with the study. On

arrival to the operating room, the patient again will be given time to ask any question. A written informed consent is required before randomization.

Withdrawal from the study: A patient can at any time without reason withdraw their consent. The patient will be asked, if previously collected data can be used, and whether it is acceptable to follow them in the registries, even though they don't want to meet to follow-up visits. Otherwise data will be deleted. The patient's decision to withdraw will be filed in the patient record.

Ethical aspects, risk, side effects, benefit and harm when participating in the study:

It is not expected that any risk is associated with participation in the study. The procedures compared are routine procedures and only high-volume centers will participate, and patients will only be included if a heart team conference have found them eligible for treatment with the study valves.

None the less it is important to continuously monitor safety and quality of the valves. The present study will ensure continuous head-to-head comparisons of valves used routinely. There is no potential benefit for the single patient when participating. Scientifically, the benefit is quality assessment of the valves used routinely and publication of long-time follow-up. In case a valve performs inferior to its comparator, appropriate consequences will be taken. Historically, there are examples (Mitroflow surgical valve) that valves used for several years degenerated earlier than expected.

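### Minor, cheap improvement: compare 6-minute walk distance by baseline-adjusted ANCOVA, fixed in advance, rather than by an unadjusted t-test or Mann-Whitney test chosen on normality

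*Combined protocol and SAP*

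**What the plan says.** Hypothesis 2 lists the walk test among the endpoints on which the valves are expected not to differ: "new pacemaker implantation, readmission for congestive heart failure, 6-minute walk test". Item 8 of the secondary endpoints gives the schedule: "6-minute walk test: baseline, 30-day, 1-year, 3-year, 5-year and 10-year".

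The paragraph headed Statistics is the only text on analysis methods. Continuous data are summarised by mean and SD and "compared using a t-test, if data are normally distributed. If data are not normally distributed the Mann Whitney U test will be used". It adds: "When comparing secondary endpoints, Cox regression and logistic regression analyses will be used, as appropriate". Neither of those regressions fits a distance in metres, so the t-test and the Mann-Whitney test are what remains for this endpoint.

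The document names no linear regression, ANCOVA or repeated-measures model, defines no change from baseline, and names no covariate for the walk test. It gives no SD, correlation, target difference or expected attendance for it either.

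**The concern.** Patients perform a baseline walk, but the plan does not say how that measurement enters the comparison of valves. Two things are left open:

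- whether follow-up distances or changes from baseline are compared;
- whether the result is a difference in means or a comparison of ranks. That depends on a normality judgement made once the data are in, with no criterion given, and it could come out differently at different visits.

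At stake is precision on one secondary endpoint, and a comparison fixed before the data are seen. The trial is unblinded and each time point is published separately, so fixing the comparison in advance has some value. Type I error on the primary endpoint, its sample size and its non-inferiority margin are not involved.

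**Working it through.** **Inputs.** The plan has no walk-test figure to reproduce. Cohort B size comes from Power calculations: "If including 1062 patients as planned in cohort B, and with no interim analyses and 5% drop-out". The allocation ratio is not stated, so 1:1 is assumed. The sample-size table supports this: for a 7% event rate and a 4% margin, 2 × 0.07 × 0.93 × (1.645 + 0.842)² / 0.04² = 503.1, so 504 per arm and 1008 in total, as tabulated. The correlation r between baseline and follow-up distance, the distribution and the attendance are all assumptions.

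**Step 1: variance against the t-test.** For large samples, 1:1 allocation, equal SDs and the same patients, relative to a t-test on follow-up values:

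- t-test on follow-up values: 1
- t-test on changes: 2(1 − r)
- ANCOVA: 1 − r²

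ANCOVA relative to changes is therefore (1 − r²) / [2(1 − r)] = (1 + r)/2. Neither ratio can exceed 1.

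| Assumed r | 1 − r² | SE reduction vs follow-up t-test | (1 + r)/2 | SE reduction vs change t-test |
|---|---|---|---|---|
| 0.3 | 0.91 | 5% | 0.65 | 19% |
| 0.5 | 0.75 | 13% | 0.75 | 13% |
| 0.7 | 0.51 | 29% | 0.85 | 8% |
| 0.8 | 0.36 | 40% | 0.90 | 5% |

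**Step 2: what this means in cohort B.** The 95% CI half-width in SD units is 1.96 × √(2 × factor / n), with n = 1062 × f / 2 per arm and f the fraction tested.

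| Fraction tested | n per arm | Follow-up t-test | ANCOVA at r = 0.3, 0.5, 0.7, 0.8 |
|---|---|---|---|
| 95% | 504 | 0.123 | 0.118, 0.107, 0.088, 0.074 |
| 70% | 372 | 0.144 | 0.137, 0.125, 0.103, 0.086 |
| 50% | 266 | 0.170 | 0.162, 0.147, 0.121, 0.102 |

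The 95% row borrows the 5% drop-out used for the primary endpoint and is a best case, because a walk test needs attendance. The 70% and 50% rows are hypothetical.

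**Step 3: against the Mann-Whitney branch.** For a location shift, Mann-Whitney efficiency relative to the t-test is 3/π = 0.955 with normal data and 1.5 with double-exponential data. The efficiency of ANCOVA relative to Mann-Whitney is [1/(1 − r²)] divided by that figure. At r = 0.3, 0.5, 0.7, 0.8:

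- normal: 1.15, 1.40, 2.05, 2.91
- double exponential: 0.73, 0.89, 1.31, 1.85, with break-even at r = √(1 − 1/1.5) = 0.58

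A simulation with 372 per arm, a shift of 0.15 SD and double-exponential data (4000 runs per cell) gave power of 0.70, 0.70, 0.70, 0.71 for Mann-Whitney and 0.57, 0.64, 0.80, 0.92 for ANCOVA.

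**Step 4: conditions.** *Allocation.* In a simulation with 1009 patients, 3:1 allocation and opposite slopes in the two arms, the SE was 0.0920 for the t-test, 0.0921 for plain ANCOVA and 0.0817 with a valve-by-baseline interaction. Outside 1:1, the guarantee therefore needs the interaction term. *Missing baseline.* If a fraction m of tested patients has no baseline walk and is dropped, the ANCOVA ratio becomes (1 − r²)/(1 − m), which exceeds 1 once m > r²: 9% at r = 0.3 and 25% at r = 0.5. If those patients are kept with a mean-imputed baseline, and missingness is unrelated to distance, the ratio is about (1 − m)(1 − r²) + m = 1 − (1 − m)r², which stays at or below 1.

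**The case against.** The strongest reply is that this is a preference. An unadjusted comparison of randomised arms is valid, the walk test is one of 27 listed secondary endpoints, no power is claimed for it, and the size of the gain rests wholly on an assumed r. All of that is true, and it is why the point is minor. It does not remove the point: a baseline already scheduled for collection can sharpen the comparison, and the plan leaves the comparison itself unspecified.

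Three stronger readings are tempting and are not supported.

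- *That baseline distance is used in no analysis.* The general rule for continuous data could cover describing baseline distance by arm, or comparing changes. What the text supports is narrower: no use as a covariate is stated, and the choice between follow-up values and changes is not made.
- *That adjustment is free or always better.* It needs the allocation and same-patients conditions of Step 4, and it gives no guarantee against Mann-Whitney. The document does not show which branch will apply.
- *That ANCOVA deals with incomplete walk tests.* It does not remove bias if death or missed tests differ by valve. Nor does the document establish poor attendance. The statement "Follow-up (30-day, 1-year, 3-year, 5-year and 10-year) will be conducted mainly registry based" concerns follow-up in general, and patients who may stay in the registries "even though they don't want to meet to follow-up visits" are those withdrawing consent. How many patients are tested, dead or untested per arm is a separate reporting matter and adds no weight here.

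**Conclusion.** The point holds as a minor, cheap improvement. The plan schedules a baseline walk but specifies no adjustment for it, and it leaves both the scale (value or change) and the type of comparison (means or ranks) open. Against either t-test, ANCOVA is at least as precise in large samples, given the same patients and either 1:1 allocation (assumed) or a valve-by-baseline interaction. The saving in standard error over a follow-up t-test is about 5% to 40% for assumed r of 0.3 to 0.8. The documents do not show where in that range the trial lies. With heavy tails and r below about 0.58 the planned rank test could be the more powerful choice. A reader should not infer that the planned tests are wrong, or that the primary endpoint or sample size is affected.

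**What to change.** In Statistics, before the walk-test comparison is run, state that:

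1. walk distance at each visit is compared by ANCOVA of follow-up distance on valve and baseline distance, with a centred valve-by-baseline interaction if allocation is not 1:1;
2. the adjusted mean difference is reported with its 95% CI;
3. patients without a baseline walk stay in the model by simple imputation of the baseline value, for example the mean over both arms;
4. the Mann-Whitney test is a pre-stated sensitivity analysis at every visit, replacing the switch on normality.

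The cost is three or four sentences. No new data or visits are needed, and the sample size and primary analysis do not change. The price to accept is the possible loss of power against the rank test in the heavy-tailed, low-correlation case; item 4 keeps that result in view.

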Funds will be applied for support of the study. Each of the company's manufacturing TAVI valves will be applied for support. The companies will have no influence on the design or conduction of the study. If a grant is given the Ethical committee will be informed and any contract should be approved by Aarhus University Hospital. No honorary is given to the patients nor to the physicians responsible for the study. Any grant will be used to the conduct of the study, salary to study nurses/secretaries and presentation of data.

So far cohort B has been sponsored by Meril, The Danish Heart Foundation and Vingmed Vicare.

For new cohorts, the company providing the comparator valve will be applied for a grant to sponsor to cover all expenses in the study (payment of site, monitoring, various committee meetings, core-labs).

Publications:

Each cohort will be published after inclusion of 1.346 patients in case interim analysis is decided or 1.062 patients if no interim analysis is decided, independent of the final findings. If a valve is retracted from clinical use, or the safety committee advocates for pre-term termination of randomization, data will be published at this time. First authorship is given to the center with the highest number of included patients. Number of co-authorships to each center is given according to number of included patients. Core-labs are acknowledged with co-authorships. For each cohort, one physician is responsible for initiating the cohort and senior author on the paper. A separate publication will be performed for 30-day, 1-year, 3-year, 5-year and 10-year data.

Reference list:

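### The non-inferiority table has 80% power only at one-sided 5%, but the only sidedness the plan states is double-sided 5%, at which power is about 70–72%

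*Combined protocol and SAP*

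**What the plan says.** **Statistics.** After listing the tests for continuous and categorical data, the section states: "Significance level is $p<0.05$ (double sided). When comparing primary endpoints, a non-inferiority analysis will be used". It gives the non-inferiority analysis no level, interval or decision rule of its own, and no other section does so.

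**Power calculations, table header.** "Power=0.80. Alfa=0.05". Sidedness is not given.

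**Power calculations, text.** For cohort B, with 1062 patients, no interim analyses and 5% drop-out, "the non-inferiority margin would be 4% if the event-rate is 7% and 4.5% if the event rate is 9" percent. The design with two interim analyses has 1346 patients at a 9% event rate and a 4% margin. If the observed event rate departs from the expected one, "the steering committee should consider adjusting sample size or non-inferiority margin", and the reader is sent back to the same table.

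**Power calculations, MRI sub-study.** "A total of 148 patients are needed to document a difference of 0.25" cm² in EOA, and "102 patients to document a difference of 0.05 in expected regurgitation fraction". This paragraph states neither alpha nor power.

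**Publications.** The two sizes are fixed as publication triggers: "1.346 patients in case interim analysis is decided or 1.062 patients if no interim analysis is decided".

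**The concern.** A non-inferiority claim is made when one confidence limit for the risk difference lies inside the margin. An unlabelled alpha of 0.05 can mean the upper limit of a 90% interval (one-sided 5%) or of a 95% interval (double-sided 5%, so 2.5% in the direction that matters). The two give different power for the same number of patients, and different verdicts on the same data.

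The plan states a power that belongs to the first rule. The only sidedness it states leads to the second. If the analysts follow the Statistics section as written, the 80% is too favourable. If they use a 90% interval, the 80% is right, but they are applying a rule the plan does not contain.

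The trial is unblinded (Blinding section), so the level should not be left to be chosen once results are visible. Any new size or margin that the steering committee reads from the table would carry the same unlabelled level.

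**Working it through.** **Inputs.** Event rates, margins, sizes, 80% power and alpha 0.05 come from the Power calculations table. Two inputs are assumed because the plan does not state them numerically: 1:1 allocation and equal true event rates. Both are supported by the fact that they reproduce the table.

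**Step 1: reproduce the table.** Total N = 2 × ceil[(z + 0.8416)² × 2p(1−p) / margin²], with z = 1.645 for one-sided 5% and z = 1.960 for double-sided 5%. For 7% and a 4% margin:

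- One-sided: 6.183 × 0.1302 / 0.0016 = 503.1, so 504 per arm and 1008 in total.
- Double-sided: 7.849 × 0.1302 / 0.0016 = 638.7, so 639 per arm and 1278 in total.

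| Event rate / margin | Table (no drop-out, no interim) | One-sided 5% | Double-sided 5% |
|---|---|---|---|
| 7% / 4% | 1008 | 1008 | 1278 |
| 9% / 4% | 1268 | 1266 | 1608 |
| 11% / 4% | 1514 | 1514 | 1922 |
| 13% / 4% | 1750 | 1750 | 2220 |
| 7% / 4.5% | 796 | 796 | 1010 |
| 9% / 4.5% | 1002 | 1002 | 1270 |
| 11% / 4.5% | 1198 | 1196 | 1518 |
| 13% / 4.5% | 1382 | 1382 | 1754 |

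Six cells match exactly at one-sided 5% and two differ by 2 patients. None matches at double-sided 5%, where the sizes are about 27% larger (7.849 / 6.183 = 1.27). The cohort B row (1009 at 9%) is consistent with this: its margin is rounded, and the exact one-sided 5% margin at that size is 4.48%.

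**Step 2: power at the planned sizes.** Power = Φ(margin / √[4p(1−p)/N] − z). Cohort B after drop-out has 0.95 × 1062 ≈ 1009 evaluable patients. For 9% and 4.5%, the standard error is √(4 × 0.09 × 0.91 / 1009) = 0.01802 and 0.045 / 0.01802 = 2.497. Power is Φ(0.853) = 80.3% at z = 1.645 and Φ(0.537) = 70.5% at z = 1.960.

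| Cohort B | 1009 evaluable: 90% CI / 95% CI | 1062, no drop-out: 90% CI / 95% CI |
|---|---|---|
| 7% / 4.0% | 80.1% / 70.2% | 81.8% / 72.4% |
| 9% / 4.5% | 80.3% / 70.5% | 82.1% / 72.6% |
| 11% / 5.0% | 81.4% / 71.8% | 83.1% / 74.0% |
| 13% / 5.3% | 80.5% / 70.6% | 82.2% / 72.8% |

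The cohort A design at 9% / 4%, treated as a fixed sample because no stopping boundary is given, has 0.95 × 1346 ≈ 1279 evaluable patients: 80.4% against 70.5%. If all 1346 are analysed, the figures are 82.1% against 72.7%.

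**Step 3: check without the power approximation.** Exact binomial enumeration of Wald limits with 505 and 504 patients, 9% in both arms and a 4.5% margin gives 80.3% against 70.5%. So about 10% of trials of truly equal valves pass at 90% and fail at 95%. With true rates of 13.5% and 9%, exactly at the margin, the false-positive rate is 5.1% against 2.6%.

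**Step 4: an example.** Take 45/504 events in one arm and 51/505 in the other. The difference is 10.10% − 8.93% = 1.17%, with standard error 1.85%. The upper limit is 1.17 + 1.645 × 1.85 = 4.2% at 90% and 1.17 + 1.960 × 1.85 = 4.8% at 95%. Against 4.5%, the first passes and the second fails. The same split occurs with 50 or 52 events.

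**Step 5: the MRI sizes.** N = 2 × ceil[2(z + 0.8416)² × SD² / difference²], with 80% power assumed.

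- EOA (SD 0.54, difference 0.25): 73.2 per arm before rounding at double-sided 5%, giving 148; one-sided 5% gives 116.
- Regurgitation fraction (SD 0.09, difference 0.05): 50.9 per arm before rounding at double-sided 5%, giving 102; one-sided 5% gives 82.

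The stated 148 and 102 are double-sided. The Power calculations section therefore uses both conventions and labels neither.

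**The case against.** The strongest reply is that there is no real conflict. The phrase "Significance level is $p<0.05$ (double sided") closes a list of ordinary difference tests, and the non-inferiority sentence comes after it. A non-inferiority test against one margin is one-directional by nature, so alpha 0.05 in a table for non-inferiority designs can be read as one-sided. The MRI sizes fit that account: double-sided for documenting a difference, one-sided for non-inferiority. On this reading the 80% is correct and only labels are missing.

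Much of this stands. The reading is possible, the MRI pattern favours it, and the table's arithmetic is not at fault. Using different conventions for different kinds of test is no error in itself. But the reading is not written down. The double-sided level carries no exception and immediately precedes the primary analysis. A reader can reach the benign interpretation only by rebuilding the sample-size formula, and the rule that decides the primary conclusion should not depend on that.

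Two limits of scope also stand. The columns with two interim analyses could not be rebuilt without a boundary, so the cohort A powers are fixed-sample figures. Cohort A is also listed as not yet recruiting, so the immediate effect falls on cohort B.

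**Conclusion.** The concern holds. The primary sample sizes deliver 80% power at one-sided 5%, while the only sidedness the plan states is double-sided. Applied literally, through the upper limit of a 95% interval, that level gives cohort B 70.2–71.8% power with the planned 5% drop-out and 72.4–74.0% with none. This is a loss of roughly 10 percentage points against the 90% interval. The one-directional error rate at the margin is about 5% on one reading and 2.5% on the other.

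The loss is conditional: it disappears if a 90% interval is declared. The figures assume 1:1 allocation, equal true rates and unpooled variances. It must be fixed because the choice decides the primary verdict for a band of plausible results.

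**What to change.** Make the Statistics section and the table agree, in a dated change made before any comparative data are read. Either option would do.

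- **(a) Declare one-sided 5%.** State that the primary non-inferiority test is one-sided at 5%, judged on the upper limit of the two-sided 90% confidence interval for the risk difference, and that the double-sided level applies to the other comparisons. Label the table as one-sided alpha 0.05. Cost: one sentence and one label. The plan then openly accepts a 5% rather than 2.5% one-directional error rate. Sizes, margins and the 80% are unchanged.
- **(b) Keep double-sided 5%.** State that the primary test uses the upper limit of the two-sided 95% interval, leave the stated margins alone, and restate the power of the 1062 and 1346 designs as about 70% (cohort B 70.2–71.8% after drop-out; the 1346 design 70.5% at 9% / 4%, ignoring interims). Cost: one sentence and a less favourable power figure.

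Under (b), the margins that would have 80% power at 1009 evaluable patients (4.5, 5.05, 5.5 and 5.9% for event rates of 7, 9, 11 and 13%) may be shown for information. They should not be adopted as a relabelling, because a wider margin changes what counts as non-inferior.

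Under either option, state the sidedness, alpha and power of the MRI calculation too. No added patients and no operational change are needed.
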